6.2 Randomization

The randomization sequence will be obtained by computer-generated random numbers and provided to each HVTN CRS through the SDMC via a Web-based randomization system. Participants will be randomized to either one of Groups 1-3 or one of Groups 4-5, depending on site. The randomization will be stratified by sex at birth and done in blocks to ensure balance. All participants will be randomized prior to the first infusion, ideally within 4 days. Once enrollment has stopped in Groups 3 and 5, participants will then be randomized to either one of Groups 1 and 2 or be enrolled in Group 4, depending on site. At each institution, the pharmacist with primary responsibility for dispensing study products is charged with maintaining consistency of the treatment assignments.

6.3 Blinding

The study will be open label.

6.4 Statistical analysis

This section describes the final study analysis. Of note, Groups 1-3 participants are enrolled 1 month before the first infusion. Groups 4 and 5 participants are enrolled at the first infusion. All analyses pertaining to the safety and drug level objectives of this study are intent-to-treat analyses that include all randomized individuals per their randomization allocation. In addition, analyses will also be performed as treated accounting for the actual infusions and dose levels each participant received.

Analyses will be performed using SAS and R. Other software may be used to perform additional exploratory pharmacokinetics analyses.

No formal multiple comparison adjustments will be employed for multiple safety endpoints.

6.4.1 Analysis variables

The analysis variables consist of baseline participant characteristics, safety, and laboratory measurements for primary- and secondary-objective analyses.

6.4.2 Baseline comparability

Treatment arms will be compared for baseline participant characteristics using descriptive statistics.

6.4.3 Safety/tolerability analysis

All participants who received at least 1 partial or complete infusion will provide some safety data.

6.4.3.1 Reactogenicity

The number and percentage of participants experiencing each type of reactogenicity sign or symptom will be tabulated by severity and treatment arm and the percentages displayed graphically by arm. For a given sign or symptom, each participant's reactogenicity will be counted once under the maximum severity for all infusion visits. In addition, to the individual types of events, the maximum severity of local pain or tenderness, induration or erythema, and of systemic symptoms will be calculated.

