6.4.3.3 Local laboratory values

Boxplots of local laboratory values will be generated for baseline values and for values measured during the course of the study by treatment arm and visit. Each boxplot will show the first quartile, the median, and the third quartile. Outliers (values outside the boxplot) will also be plotted. If appropriate, horizontal lines representing boundaries for abnormal values will be plotted.

For each local laboratory measure, summary statistics will be presented by treatment arm and timepoint, as well as changes from baseline for postenrollment values. In addition, the number (percentage) of participants with local laboratory values recorded as meeting Grade 1 AE criteria or above as specified in the DAIDS AE Grading Table (see Section 11.2) will be tabulated by treatment arm for each postinfusion timepoint. Reportable clinical laboratory abnormalities without an associated clinical diagnosis will be included in the tabulation of AEs described above.

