7.1 Inclusion criteria

General and Demographic Criteria

1. **Age** of 18 to 50 years
2. **Weight** \leq 115 kg
3. **Access to a participating HVTN CRS** and willingness to be followed for the planned duration of the study
4. Ability and willingness to provide **informed consent**
5. **Assessment of understanding**: volunteer demonstrates understanding of this study; completes a questionnaire prior to enrollment with verbal demonstration of understanding of all questionnaire items answered incorrectly
6. **Agrees not to enroll in another study** of an investigational research agent until completion of the last study visit
7. **Good general health** as shown by medical history, physical exam, and screening laboratory tests

HIV-Related Criteria:

8. Willingness to receive **HIV test results**

9. Willingness to discuss HIV infection risks and amenable to HIV risk reduction counseling.
10. Assessed by the clinic staff as being at “**low risk**” for **HIV infection** [low risk guidelines are found on the protocol home page on the HVTN Members’ site (<https://members.hvtn.org/protocols/hvtn116>)] and committed to maintaining behavior consistent with low risk of HIV exposure through the last required protocol clinic visit.

Laboratory Inclusion Values

Hemogram/CBC

11. **Hemoglobin** \geq 11.0 g/dL for volunteers who were born female, \geq 13.0 g/dL for volunteers who were born male
12. **White blood cell count** = 2,500 to 12,000 cells/mm³
13. **Total lymphocyte count** \geq 800 cells/mm³
14. **Remaining differential** either within institutional normal range or with site physician approval
15. **Platelets** = 125,000 to 550,000/mm³

Chemistry

16. **Chemistry panel:** ALT, AST, and alkaline phosphatase $<$ 1.25 times the institutional upper limit of normal; creatinine \leq institutional upper limit of normal.

Virology

17. **Negative HIV-1 and -2 blood test:** US volunteers must have a negative FDA-approved enzyme immunoassay (EIA). Non-US sites may use locally available assays that have been approved by HVTN Laboratory Operations.
18. **Negative Hepatitis B surface antigen (HBsAg)**
19. **Negative anti-Hepatitis C virus antibodies (anti-HCV),** or negative HCV polymerase chain reaction (PCR) if the anti-HCV is positive

Urine

20. **Normal urine:**
 - Negative urine glucose, and
 - Negative or trace urine protein, and

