9.4 Infusion visits

At all infusion visits, the following procedures are performed before infusion:

- Abbreviated physical examination, including weight, vital signs, and a symptom-directed evaluation by history and/or appropriate physical exam based on participant self-reported symptoms or complaints;
- Assessment of baseline reactogenicity parameters;
- Assessment of concomitant medications (Section 9.2);
- Assessment of any new or unresolved AEs/intercurrent illnesses; and
- Urine or serum pregnancy test (for participants who were born female). Persons who are NOT of reproductive potential due to having undergone bilateral oophorectomy (verified by medical records), are not required to undergo pregnancy testing;
- Blood collection for serum trough levels and storage (not applicable at the first infusion visit in Groups 1-3, as baseline samples will be collected at enrollment).

Following completion of all procedures in the preceding list, and if results indicate that infusion may proceed, infusion is administered (Sections 8.3 and 8.4).

Immediately following infusion, the participant remains in the clinic for observation. An initial reactogenicity assessment is made at a target of 30 minutes after all IV infusions, with an acceptable range of 25-60 minutes. Before leaving

the clinic, the participant is given the postinfusion memory tool and is instructed on how to complete it. The site will make arrangements to obtain daily reports of reactogenicity events from the participant during the reactogenicity period (Section 9.10).

The following procedures will be performed at infusion visits as specified in [Appendix L](#), [Appendix M](#), [Appendix N](#), and [Appendix O](#). These procedures may be performed prior to, during, or following infusion:

- Risk reduction counseling (Section 9.7);
- Pregnancy prevention assessment (Section 9.2 and 9.8); and
- Assessment of new or unresolved social impacts (site staff will ask participant about the status of any unresolved social impacts and if s/he has experienced any new social impacts as a result of the trial participation).
- Administration of the social impact assessment questionnaire (types of impacts assessed involve personal relationships, health insurance, life insurance, educational or employment opportunities, housing, immigration, or travel);
- Administration of behavioral risk assessment questionnaire;
- Biopsy acceptability questionnaire;
- HSV 1/2 testing

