9.10 Assessments of reactogenicity

For all participants, baseline assessments are performed before and reactogenicity assessments are performed after infusions per SSP. All reactogenicity symptoms are graded according to the Division of AIDS Table for Grading the Severity of Adult and Pediatric Adverse Events, Corrected Version 2.1, July 2017, except as noted in Section [11.2.2](#).

The reactogenicity assessment period is 3 full days following each infusion per the assessment schedule shown in [Table 9-3](#). Participants are instructed to record symptoms using a postinfusion memory tool. Contacts between the participant and the site staff should take place daily during the assessment period. Clinic staff will follow new or unresolved reactogenicity symptoms present at day 3 to resolution. Participants are instructed to contact the clinic for events that arise during the period between infusions and the next scheduled visit. In general, a participant who self-reports any postinfusion reaction greater than mild is seen by a clinician within 48 hours after onset, unless the reaction is improving and/or has completely resolved.

Reactogenicity events are reported using CRFs that correspond to the time of assessment in [Table 9-3](#). Reactogenicity assessments include assessments of systemic and local symptoms and infusion-related lesions. Events not listed on a CRF, or with an onset after the reactogenicity assessment period (day of infusion

and 3 full days after), or those meeting SAE/adverse events requiring expedited reporting to DAIDS criteria, are recorded on an adverse event log form.

Table 9-3 Schedule of reactogenicity assessments

Day	Time	Performed by
0 ^a	Baseline: before study product administration	HVTN CRS staff
	Early: 25-60 minutes after all infusions	HVTN CRS staff
	Between early assessment and 11:59pm day 0	HVTN CRS staff or participant
1	Between 12:00am and 11:59pm day 1	HVTN CRS staff or participant
2	Between 12:00am and 11:59pm day 2	HVTN CRS staff or participant
3 ^b	Between 12:00am and 11:59pm day 3	HVTN CRS staff or participant

^a Day of study product administration

^b New or unresolved reactogenicity symptoms present on day 3 are followed until resolution

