#### 8.4.3. Local laboratory values

Boxplots of local laboratory values will be generated for baseline values and for values measured during the course of the study by treatment arm and visit. Each boxplot will show the first quartile, the median, and the third quartile. Outliers (values outside the boxplot) will also be plotted. If appropriate, horizontal lines representing boundaries for abnormal values will be plotted.

For each local laboratory measure, summary statistics will be presented by treatment arm and time point, as well as changes from baseline for post-enrollment values. In addition, the number (percentage) of participants with local laboratory values recorded as meeting Grade 1 AE criteria or above as specified in the DAIDS AE Grading Table (see Section 11.2 of the protocol) will be tabulated by treatment arm for each postinfusion time point. Reportable clinical laboratory abnormalities without an associated clinical diagnosis will also be included in the tabulation of AEs described above.

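### The reactogenicity tables have no rule for using the pre-infusion assessment, so a symptom already present that persists at the same grade can be counted as reactogenicity

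*Protocol*

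**What the plan says.** **Counting rule.** Protocol 6.4.3.1 tabulates solicited signs by severity and arm, and for each sign a participant's "reactogenicity will be counted once under the maximum severity for all infusion visits". SAP 8.4.1 repeats this text and adds no baseline rule. The SAP output lists (9.1, 9.2) add only maximum local and systemic reactogenicity summaries and the matching graphs.

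**What is collected.** Protocol 9.4 requires "Assessment of baseline reactogenicity parameters" ahead of each infusion. Table 9-3 gives this its own day-0 row, "Baseline: before study product administration". Protocol 9.10 states that "baseline assessments are performed before and reactogenicity assessments are performed after infusions per SSP". The assessment period is the day of infusion plus three full days, and 9.10.1 reports the daily maximum severity of each symptom.

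**Attribution.** Under Protocol 9.10, solicited events within the period go on reactogenicity forms. The adverse event log takes events not listed on those forms, later-onset events, and events meeting serious or expedited reporting criteria. The relationship-to-product tables in SAP 9.1 are for adverse experiences. None is listed for reactogenicity.

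**Laboratory values.** Participants at Grade 1 or above "will be tabulated by treatment arm for each postinfusion timepoint" (Protocol 6.4.3.3; same in SAP 8.4.3). The same section plans baseline boxplots and summary statistics "as well as changes from baseline for postenrollment values". Inclusion criterion 14 accepts the remaining differential "either within institutional normal range or with site physician approval".

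**The concern.** Safety and tolerability is primary objective 1, and the reactogenicity percentages are a main summary of it. Mild fatigue or headache is common enough in healthy adults that some participants may arrive at an infusion visit with one. If it continues at the same grade after the infusion, the counting rule as written lets it into the table.

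Two features of the design make this matter. First, no group receives placebo. The SAP's Design paragraph calls the trial placebo controlled and double-blind, but both schemas show five active groups, and Protocol 6.3 and SAP section 7 say open label. Second, participants have one, three or four infusions depending on group, and the table takes the maximum over all of them. More infusions give a background symptom more chances to be counted. Groups 2 and 4 receive the same product at the same dose, four times and once respectively. A higher percentage in Group 2 could look like an effect of repeat dosing when part of it is carried-over background.

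**Working it through.** **1. The plan's own intervals.** Table 6-2 uses the score interval: centre (p + z²/2n)/(1 + z²/n), half-width z·√[p(1−p)/n + z²/4n²]/(1 + z²/n), with z = 1.96.
- 0/23: the upper bound reduces to z²/(n + z²) = 3.8416/26.8416 = 14.31%, as stated.
- 1/23: 0.1088 ± 0.1011, which is 0.77% to 20.99%, as stated.
- All twelve rows for n = 16, 23, 39 and 62 reproduce to two decimals.

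**2. Effect of one carried-over symptom.** This needs no assumed rate.
- Group of 23: 0/23 (upper bound 14.31%) becomes 1/23 (0.77% to 20.99%). The upper bound rises by 20.99 − 14.31 = 6.68 points.
- Group of 16: 0/16 (upper bound 19.36%) becomes 1/16 (1.11% to 28.33%).

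A count referenced to the same infusion's baseline would leave both at zero.

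**3. Accumulation over infusions.** Let b be the probability, per infusion, that a given symptom is present beforehand and persists afterwards at the same grade. The documents give no value, so b is an assumption and a range is shown. Over m infusions, the share of participants counted at least once is 1 − (1 − b)^m if infusions are independent. It is b if the same participants are affected every time. For example, b = 5% and m = 4 gives 1 − 0.95⁴ = 18.5%, or 4.3 of 23.

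| Assumed b | One infusion (Group 4, n = 16) | Three, independent (Group 3) | Four, independent (Groups 1, 2, n = 23 each) | Four, full correlation |
|---|---|---|---|---|
| 1% | 1.0% (0.2) | 3.0% | 3.9% (0.9) | 1% (0.2) |
| 2% | 2.0% (0.3) | 5.9% | 7.8% (1.8) | 2% (0.5) |
| 5% | 5.0% (0.8) | 14.3% | 18.5% (4.3) | 5% (1.2) |
| 10% | 10.0% (1.6) | 27.1% | 34.4% (7.9) | 10% (2.3) |

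Brackets give expected participants (share times n). The truth should lie between the last two columns. Under full correlation the four-infusion and one-infusion arms are inflated equally; any weaker correlation inflates the four-infusion arms more.

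**4. Laboratory grades.** The Grade 1+ count has no baseline reference, but baseline is used elsewhere in the section. The grading table's cut-offs are not in the documents, so whether a value allowed at entry is Grade 1 cannot be checked.

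**The case against.** **Silence is not a rule.** A reader might infer that the plan tells the analyst to ignore baseline, or that the pre-infusion record itself enters the maximum. The documents support neither. They are silent on the first. On the second, Protocol 9.10 places reactogenicity assessments after infusion and keeps baseline apart. How a continuing symptom is recorded may be settled in the Study Specific Procedures or the forms, which are not in the documents. This stands. The gap is confined to symptoms that persist after infusion.

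**Laboratory data.** A reader might infer that permitted entry abnormalities will be reported as post-infusion events. The documents do not show it. Changes from baseline and baseline boxplots are planned, the Grade 1+ table is an additional per-timepoint count, and no permitted entry value is shown to be Grade 1. This largely disposes of the laboratory side.

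**Other controls.** Groups 1 and 2 are randomized with the same four infusions, and Groups 4 and 5 were randomized with one each, so background should fall alike within each pair. That is right for comparing dose or product. It gives no absolute background rate and does not help Group 2 against Group 4. Protocol 7.3.1 lists pre-infusion symptoms that could mask a reaction among the factors for delaying an infusion. This may reduce the problem but sets no counting rule. SAP section 5 relies on reported relationship to product, but for adverse events.

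**Convention and consequence.** Counting every post-infusion symptom errs towards over-reporting, which is defensible in phase 1. The tables are descriptive, and the pause rules in Table 11-1 act on individual related events, not on these percentages. This is a good reason to keep the any-grade table, but not to withhold a baseline-referenced one.

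**Conclusion.** The point holds for reactogenicity. Neither document says how a symptom present before infusion and persisting at the same grade is counted, and as written it can be counted as reactogenicity. With no placebo group and no attribution table for solicited events, the reader of the tables cannot remove it, and it can accumulate unequally across arms.

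The size is not fixed by the documents. For assumed b of 1–10%, the four-infusion share is 1–10% at one extreme and 4–34% at the other. A reader might take the upper figures as a forecast. They are not: they rest on unsourced rates, independence between infusions, and persistence of every such symptom with no infusion delayed. They also count participants who might have had a new reaction anyway. The firm figure is the shift from 0/23 to 1/23 caused by a single participant.

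This is worth correcting because it bears on a primary tolerability summary and the baseline assessments are already scheduled. The laboratory part is secondary and optional.

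**What to change.** In Protocol 6.4.3.1 and SAP 8.4.1, add a baseline-referenced table. Count a sign at an infusion only if its worst post-infusion grade exceeds its grade before that same infusion, then take the participant's maximum over infusions. Show it beside the existing any-grade table so that persisting symptoms stay visible, and add both to the SAP output lists.

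Optionally, in 6.4.3.3 and SAP 8.4.3, add a shift table from screening grade to worst post-infusion grade alongside the Grade 1+ tabulation.

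The cost is SAP wording, programming and one extra set of tables, with no new data, provided the baseline form records a grade for each sign. The form is not in the documents, so this should be confirmed. Symptoms persisting at an unchanged grade would appear only in the any-grade table. New-onset background symptoms unrelated to product would still be counted in both.

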Study products and routes of administration

- **VRC01:** human monoclonal antibody (mAb) VRC-HIVMAB060-00-AB in formulation buffer at pH 5.8 in sufficient normal saline (Sodium Chloride for Injection 0.9%, USP) to be administered intravenously (IV)
- **VRC01LS:** human monoclonal antibody (mAb) VRC-HIVMAB080-00-AB in formulation buffer at pH 5.8 in sufficient normal saline (Sodium Chloride for Injection 0.9%, USP) to be administered IV

Table 3-1 Schema

Group	Treatment	Infusion schedule (Months)					
		N	M0	M2	M3	M4	M6
Group 1	VRC01 10 mg/kg	23	IV Infusion	IV Infusion		IV Infusion	IV Infusion
Group 2	VRC01 30 mg/kg	23	IV Infusion	IV Infusion		IV Infusion	IV Infusion
Group 3	VRC01LS 30 mg/kg	~6*	IV Infusion		IV Infusion		IV Infusion
Group 4	VRC01 30 mg/kg	16	IV Infusion				
Group 5	VRC01LS 30 mg/kg	~6*	IV Infusion				

*Enrollment will stop in Groups 3 and 5 when ≥ 12 volunteers have been enrolled across *both* groups (see Section 6.1).

Participants

About 74 healthy, HIV-uninfected adult volunteers aged 18 to 50 years, regardless of sex or gender

Design

Multicenter, randomized, open-label trial

Duration per participant

As VRC01LS is designed to have a longer half-life than VRC01, participants who receive VRC01 will be followed for 6 months after the last product administration and participants who receive VRC01LS will be followed for 12 months after the last product administration. Specifically,

Groups 1, 2, and 5: 12 months of scheduled clinic visits

Group 3: 18 months of scheduled clinic visits

Group 4: 6 months of scheduled clinic visits

Estimated total study duration

40 months (includes enrollment and follow-up)

Investigational New Drug (IND) sponsor

DAIDS, NIAID, NIH, DHHS (Bethesda, Maryland, USA)

Study products provider

Dale and Betty Bumpers Vaccine Research Center (VRC), NIAID, NIH, DHHS (Bethesda, Maryland, USA)

Core operations

HVTN Vaccine Leadership Group/Core Operations Center, Fred Hutchinson Cancer Research Center (FHCRC) (Seattle, Washington, USA)

Statistical and data management center (SDMC)

Statistical Center for HIV/AIDS Research and Prevention (SCHARP), FHCRC (Seattle, Washington, USA)

DF/Net Research (Seattle, Washington, USA)

HVTN Laboratory Center (LC)

• HIV diagnostic laboratories

- University of Washington Virology Specialty Laboratory (UW-VSL) (Seattle, Washington, USA)
- HIV Sero-Molecular Laboratory, National Institute for Communicable Diseases (HSML-NICD) (Johannesburg, South Africa)

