6.1 Accrual and sample size calculations

Recruitment will target enrolling approximately 74 healthy, HIV-uninfected adult participants into five groups receiving IV administration of either VRC01 or VRC01LS at different schedules and/or dose levels. Groups 1 and 2 participants receive 4 infusions of VRC01 every 2 months at the 10 mg/Kg and 30 mg/Kg dose levels, respectively; Group 3 participants receive 3 infusions of VRC01LS every 3 months at the 30 mg/Kg dose level; Groups 4 and 5 participants receive a single infusion of VRC01 or VRC01LS, respectively, at the 30mg/Kg dose level. Because Groups 1-3 will be enrolled at different sites from Groups 4 and 5, Groups 1-3 were originally randomized with a ratio of 1:1:1, stratified by sex at birth and, separately, Groups 4 and 5 were also originally randomized with a ratio of 1:1 stratified by sex at birth. Groups 3 and 5 will stop enrolling once a minimal number of 12 participants, regardless of sex at birth, are enrolled. At that point, Groups 1 and 2 will be randomized together with a ratio of 1:1, stratified by sex at birth. Groups 1 and 2 will still be enrolled at different sites from Group 4. Groups 1 and 2 (n=23/group) will now be randomized with a ratio of 1:1, stratified by sex at birth. A total of 10 male and 13 female participants will still be enrolled in each of Groups 1 and 2. In Groups 1-3, enrollment is concurrent with the first biopsy procedure(s). In Groups 4-5, enrollment is concurrent with the first infusion. For all groups, randomization occurs prior to the first infusion, ideally within 4 days.

All participants receiving the first complete or partial infusion will provide some safety data. However, for PK analyses of drug levels in serum and mucosa, it is possible that data may be missing for various reasons, such as participants terminating from the study early, or problems in obtaining or shipping specimens. For this reason, the sample size calculations in Section 6.1.2 account for 15% enrolled participants having missing data for the primary lab data endpoint.

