6.4.3.2 AEs and SAEs

AEs will be summarized using MedDRA System Organ Class and preferred terms. Tables will show by treatment arm the number and percentage of participants experiencing an AE within a System Organ Class or within preferred term category by severity or by relationship to study product. For the calculations in these tables, a participant with multiple AEs within a category will be counted once under the maximum severity or the strongest recorded causal relationship to study product. Formal statistical testing comparing arms is not planned since interpretation of differences must rely heavily upon clinical judgment.

A listing of SAEs reported to the DAIDS Regulatory Support Center (RSC) Safety Office will provide details of the events including severity, relationship to study product, time between onset and last infusion, and number of infusions received.

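### Reactogenicity and AE percentages are worst-ever by arm, but arms differ by design in infusions and follow-up, so crude percentages are not comparable between most arms

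*Protocol*

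**What the plan says.** Protocol 6.4.3.1, repeated in SAP 8.4.1, tabulates and graphs reactogenicity as the percentage of participants by arm, each participant being "counted once under the maximum severity for all infusion visits". Protocol 6.4.3.2, repeated in SAP 8.4.2, gives AE percentages by arm under a similar rule: "a participant with multiple AEs within a category will be counted once under the maximum severity". Neither rule has a time cut-off or a person-time denominator.

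Exposure differs by design. Protocol 6.1 states that "Groups 1 and 2 participants receive 4 infusions of VRC01 every 2 months", that "Group 3 participants receive 3 infusions of VRC01LS every 3 months", and that "Groups 4 and 5 participants receive a single infusion of VRC01 or VRC01LS". Protocol Section 3 (duration per participant) gives "Groups 1, 2, and 5: 12 months of scheduled clinic visits", "Group 3: 18 months of scheduled clinic visits" and "Group 4: 6 months of scheduled clinic visits".

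SAP 9.1 and 9.2 list maximum reactogenicity summaries and AE tables by severity and by relationship. They list no table by infusion number, no first-infusion table, no common time window and no rate per person-time.

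Some safety output does take account of exposure or time. Laboratory grades are tabulated by post-infusion timepoint. The SAE listing gives the number of infusions received and the time since the last one.

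**The concern.** Each infusion opens a new 3-day reactogenicity window (Protocol 9.10), so arms have one, three or four chances to record a reaction. AEs accrue over whatever follow-up an arm has. A worst-ever percentage therefore mixes the product and dose with the number of infusions and the time observed.

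Primary objective 1 is safety and tolerability, and the plan leaves the reading of arm differences to clinical judgment. These tables are what that judgment works from. A reader cannot recover a first-infusion or equal-time percentage from a worst-ever table.

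**Working it through.** **The plan's own figures.** The documents give no figure for the effect of unequal exposure. The nearest is the one-trial-per-participant binomial model in Protocol 6.1.1. The rate giving a 90% chance of at least one event is 1 − 0.1^(1/n). This gives 13.40% for n=16 (stated 13.39%), 9.53% for n=23 (stated 9.52%), 5.73% for n=39 (stated 5.72%) and 3.65% for n=62 (stated 3.50%, at which the chance is about 89%). The model has no term for infusions or time.

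**Exposure by arm** (Protocol Section 3 and 6.1; safety-laboratory draws after first infusion counted from Appendices L to O):

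| Group | Product | Infusions | Months | Laboratory draws |
|---|---|---|---|---|
| 1 | VRC01 10 mg/kg | 4 | 12 | 5 |
| 2 | VRC01 30 mg/kg | 4 | 12 | 5 |
| 3 | VRC01LS 30 mg/kg | 3 | 18 | 4 |
| 4 | VRC01 30 mg/kg | 1 | 6 | 2 |
| 5 | VRC01LS 30 mg/kg | 1 | 12 | 2 |

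The draws matter because reportable laboratory abnormalities without a clinical diagnosis enter the AE tables (Protocol 6.4.3.3).

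**Pairs of arms.**
- Groups 1 and 2 match on infusions and follow-up.
- Groups 4 and 5 match on infusions, but follow-up is 6 against 12 months.
- Groups 3 and 2 differ on both: 3 against 4 infusions, 18 against 12 months.
- Groups 2 and 4 have the same product and dose, but 4 against 1 infusions and 12 against 6 months.

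**Reactogenicity.** The documents give no risk per infusion, so p is assumed. If infusions are independent, P(at least one reaction in k infusions) = 1 − (1 − p)^k.

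| p | k=1 | k=3 | k=4 |
|---|---|---|---|
| 5% | 5.0% | 14.3% | 18.5% |
| 10% | 10.0% | 27.1% | 34.4% |
| 20% | 20.0% | 48.8% | 59.0% |

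Reactions in one person are probably correlated. A beta-binomial model with p=10% gives 10.0%, 20.8% and 24.3% at correlation 0.3. At 0.5 it gives 10.0%, 17.3% and 19.4%: with a=0.1 and b=0.9, P(none in 3) = 0.9 × 0.95 × 0.967 = 0.827, and multiplying by 0.975 gives 0.806 for 4. At 0.8 it gives 10.0%, 12.8% and 13.5%. The gap closes only at correlation 1.

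**AEs.** With an assumed risk q per 6 months and constant hazard, P(at least one AE in m months) = 1 − (1 − q)^(m/6).

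| q | 6 months | 12 months | 18 months |
|---|---|---|---|
| 10% | 10.0% | 19.0% | 27.1% |
| 20% | 20.0% | 36.0% | 48.8% |
| 50% | 50.0% | 75.0% | 87.5% |

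**Direction in the 30 mg/kg product contrasts.** In Group 3 against 2 and in Group 5 against 4, the VRC01LS arm is followed 6 months longer, so crude AE percentages would be expected to run against VRC01LS. For reactogenicity, Group 2 has one more infusion than Group 3, so that bias runs the other way. Group 5 against 4 has no such bias.

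**The case against.** The strongest reply is that nothing here is a comparative analysis. The stated goal is to identify safety concerns, no test between arms is planned, and a worst-grade table by regimen correctly answers what each regimen produced. This stands as far as type I error goes, and it is why the worst-grade tables should stay. It does not make the arms comparable for a reader who sets them side by side.

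The plan also promises as-treated analyses reflecting infusions actually received (Protocol 6.4, SAP 8). It defines no per-infusion or person-time safety measure for them, and the sentence addresses departures from assignment, not differences built into the schedule. SAP Section 5 deals with chance imbalance in unrelated events, which is a different matter.

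A reader might infer more than the documents support:
- That every safety display is ever/never. The laboratory tables and the SAE listing are not.
- That all VRC01LS arms are followed longer than all VRC01 arms. Group 5 has the same 12 months as Groups 1 and 2.
- That Group 3 will show the most AEs and Group 4 the fewest. Biopsies can also cause AEs, and Group 4 has five biopsy visits within about 6 months of infusion. Groups 1 and 2 have five over about a year, one of them before any infusion. Groups 4 and 5 are also enrolled at different sites from Groups 1 to 3. With 7 and 10 VRC01LS participants (SAP schema), chance could reverse any ordering: Protocol Table 6-2 gives 1/7 an interval of 3% to 51%.

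**Conclusion.** The point holds as one of presentation and interpretation. Crude reactogenicity percentages are comparable for Groups 1 and 2, for Groups 4 and 5, and for no other pair except Groups 1 or 2 with arms of equal infusion count, of which there are none. For AEs, only Groups 1 and 2 match on both infusions and follow-up.

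Under the assumed risks, identical products could differ by some 9 to 24 percentage points on reactogenicity between one and four infusions (p=10%, correlation 0.5 down to 0), and by about 29 points on AEs between 6 and 18 months (q=20%). These sizes rest on assumed risks, the correlation within a participant, and a constant AE hazard. They show what could happen and do not forecast the trial's results. The AE and reactogenicity biases do not point the same way for VRC01LS. The existence of the imbalance rests only on the schedule.

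**What to change.** Keep the worst-grade tables and add the following.

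- **SAP 8.4.1 and 9.1:** reactogenicity after the first infusion, which is common to all arms, and by infusion number.
- **SAP 8.4.2 and 9.1:** AE rates per person-year by arm.
- **SAP 8.4.2 and 9.1:** an AE table from first infusion to before Day 56. In that window every arm has had exactly one infusion (the next are scheduled at Day 56 in Groups 1 and 2 and Day 84 in Group 3), and each has one safety-laboratory draw, in Days 1 to 15. Show AEs related to mucosal sampling separately, because only Groups 4 and 5 have biopsies in this window.
- **Text with the tables:** say that crude percentages over all follow-up are not comparable between arms, and that Groups 4 and 5 were enrolled at different sites from Groups 1 to 3.

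A 6-month window would not do the same job: by Day 168 Groups 1 and 2 are scheduled for four infusions, Group 3 for three, and Groups 4 and 5 for one.

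The cost is SAP wording and a few extra tables from data already collected. Person-year rates equalise time only if the hazard is roughly constant, and they will be imprecise in the small VRC01LS arms. With full follow-up, Group 3 contributes 7 × 1.5 = 10.5 person-years and Group 5 contributes 10 × 1 = 10.
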